9.4 RISK-BENEFITS

The selected dose range for study in TR03ext of 30 mg BID to 180 mg BID were chosen given the safety profile summarized in [Section 3.3.2](#) and discussed further in [Section 9.2](#) as well as detailed in the Investigator Brochure. As summarized in, [Section 3.1.3.3](#), open label data from the TR01 study showed that pruritus suppression in the HD patients was noted with drug administration within the dose range that is planned for the current study.

Data obtained from a previous study in osteoarthritis patients dosed up to 180 mg BID with nalbuphine HCl ER tablets showed that objective opioid withdrawal symptoms at the termination of 3 weeks of therapy were absent or mild in degree (See the Investigator Brochure Section 5.4.4.5 for details).

It should be noted that the commercially available nalbuphine HCl for Injection product in the United States (Nalbuphine HCl package insert) has a usual recommended dose of 10 mg for a 70 kg adult, administered subcutaneously, intramuscularly, or intravenously, which may be repeated every 3 to 6 hours as necessary (i.e., up to a daily dose of 40-80 mg IV); and, in non-tolerant individuals, the recommended single maximum dose is 20 mg, with a maximum total daily dose of 160 mg. Exposure following IV administration is approximately 6-fold higher than following oral administration (estimated oral bioavailability of nalbuphine HCl = 16%). Therefore, a 10-mg, 20-mg, or 160-mg IV dose would correspond to approximately 60 mg, 120 mg, and 960 mg oral nalbuphine, respectively. The highest dose proposed in the TR03 study is 180 mg BID (360 mg daily dose), and this oral dose is well below the highest recommended daily treatment of 160 mg IV (equivalent to 960 mg oral) for the current marketed product.

The risk for patients participating in the study is judged to be low based on previous experience with nalbuphine oral tablets. In addition, in the current study, there will be a low initiation dose of 30 mg, a slow dose titration rate, and careful safety monitoring of patients during the clinical study.

There is no approved therapy for prurigo nodularis related pruritus in the United States or Europe. Should nalbuphine prove effective, patients with prurigo nodularis could potentially see benefit.

9.5 STUDY OVERVIEW

This is an open label safety and tolerability extension study for patients who have completed study TR03. Patients will either enter directly a drug Treatment Period (Worst Itch NRS greater than or equal to 5 (≥ 5)) or enter an extended screening period of a no-drug Observation Period (Worst Itch NRS less than 5 (<5)) based on their reported NRS scores on the first Visit (Visit 1a). For up to 12 extended screening weeks, patients in the no-drug Observation Period may also transition into the drug Treatment Period if their Worst Itch NRS increases to greater than or equal to 5 (≥ 5).

The total study duration for any individual patient will be up to 53 weeks. For patients who enter directly into the Treatment Period, the total amount of time on drug will not exceed 50 weeks. For patients who enter the Treatment Period from the Observation Period, the total amount of time spent in the combined two periods of the study cannot exceed 50 weeks. All patients who received drug treatment will have a 2-week Washout and Safety Follow-up period at the end of the dosing period, unless consent is withdrawn.

The total amount of time in the Observation Period cannot exceed 12 weeks. After 12 extended screening weeks, subjects not eligible for the Treatment Period are screen failed from the study. The study periods are summarized below in [Table 2](#).

Table 2: TR03ext Study Periods

Study Period	Study Weeks	Duration
Observation Period	
Patients who do not meet the criteria to start Treatment are followed in Observation Period visits for up to 12 extended screening weeks. During this time, the patient may meet criteria and become eligible to enter the Treatment Period. If the patient does not meet the criteria to enter the Treatment Period by the end of 12 extended screening weeks (OV12), participation in the study ends and the patient is screen failed.
	Up to 12 extended screening weeks
Treatment Period	
For patient directly entering the Treatment Period as of Visit 1a, the Treatment Period begins with Study Week 1 (Visit 1a) and ends with Study Week 50
 
For patients entering the Treatment Period after being followed in the Observation Period, the number of weeks on treatment and the end of the Treatment Period varies; Table 8 calculates the Treatment Visit assignments for any patient entering the Treatment Period from the respective Observation Period visits.
 
The End of Treatment Visit will take place after the patient completes the last week of study drug.
	Up to 50 weeks
Washout and Safety Follow-Up Period	
The Washout and Safety Follow-up Period is two (2) weeks in duration.
 
For patients directly entering the Treatment Period as of Visit 1a and completing 50 weeks of study drug treatment, the Washout and Safety Follow-up Period should take place during weeks 51 and 52.
 
For patients entering the Treatment Period after being followed in the Observation Period, the number of weeks on treatment and the end of the Treatment Period varies; Table 8 calculates the Treatment Visit assignments for any patient entering the Treatment Period from the respective Observation Period visits. The Washout and Safety Follow-up Period will take place during the two (2) weeks after the patients completes the last week of study drug.
 
The Washout and Safety Follow-up Period Visit will take place in the week following the completion of the two (2) week Washout and Safety Follow-up Period.
	2 weeks

9.6 STUDY PROCEDURES

Before the initiation of study-specific procedures the patient must be given a complete explanation of the purpose of the study, evaluations to be conducted, and risks/benefits for study participation. Patients must understand the requirements of the study, provide informed consent (See [Section 9.6.1](#) and [Section 20.3](#)), agree to the study restrictions, and agree to return for the required assessments. After review of the informed consent is documented, the patient must give witnessed verbal and written consent. For this study, patients will retain their study number from study TR03.

With the exception of Visits 1a and 1b, windows for all visits will be +/-3 Days. Please see the Schedule of Events in [Appendix 1](#) for details of the Titration Period assessments and the Study Schematics Flow Charts in [Appendix 2](#). See [Section 9.7.1](#) for details of Study Drug Dosing and [Section 9.7.6.4](#) for information on the use of pre-medications with the Study Drug. Visit 6 of TR03 will serve as TR03ext Visit 1a.

Visit 1a has procedures to be done as summarized in [Section 9.6.1](#) regardless of the patient's pruritus intensity score. Following a set of common procedures, only patients who qualify for the Treatment Period based on meeting the pruritus intensity criteria will be eligible to receive study drug; Visit 1a corresponds to TV1. For patients who, during the final visit of TR03, did not meet the pruritus intensity criteria to enter the TR03ext Treatment Period, Visit 1a corresponds to OV1, the first visit of the Observation Period. If during a subsequent observation period visit to the site, the patient meets the pruritus intensity criteria, then that observation visit immediately transitions into Visit 1b (it also corresponds to TV1 since it is now the first Treatment Period visit) – See [Section 9.6.3.3](#) and [Section 9.6.4](#).

For subjects who transition to the Treatment Period from the Observation Period, [Table 8](#) provides details on the treatment visit schedule based on the study week that the subject transitioned from the Observation Period to the Treatment Period. The subject will follow the Treatment Visit schedule outlined on the Schedule of Events ([Appendix 1](#)).

For clarity,

Patients with a Worst Itch NRS greater than 5 (≥ 5) enter the Treatment Period and will receive Study Drug starting with an evening 30 mg dose (to be taken at home), after the Visit 1a (or Visit 1b) procedures have been completed.

Receipt of the first dose of study drug will define Day 1. Visit 1a or Visit 1b for these patients is also Treatment Visit 1 (TV1). Subsequent visits will be defined as TV2, TV3, etc.

Patients with a Worst Itch NRS less than 5 (<5) enter the Observation Period and will not receive study drug treatment. Visit 1a for these patients is also Observational Visit 1 (OV1). Subsequent visits will be defined as OV2, OV3, etc.

Patients in the observation period can be followed for up to 12 weeks.

If during the Observation Period, a patient's Worst Itch NRS increases to greater than or equal to 5 (≥ 5) and the patient meets all other eligibility criteria, Visit 1b

procedures are to be performed. The patient's next visit will be Treatment Visit 2 (TV2). Do not repeat the Worst Itch NRS during Visit 1b.

If, however, at Observation Visit 12 the patient does not have a Worst Itch NRS greater than or equal to 5 (≥ 5), the patient will be screen failed without having initiated treatment with nalbuphine.

Figure 2, Figure 3 and Figure 4 visually display the relationship between TR03ext study weeks, Treatment Period weeks and Observation Period weeks.

9.6.1 Visit 1a (Day 1 of Study Week 1)

See Table 4 for summary of Visit 1a procedures. See Section 20.3 regarding the informed consent process that must take place prior to any study procedures.

Study TR03 Visit 6 procedures in common with Study TR03 extension Visit 1a procedures do not have to be repeated.

- obtain informed consent
- confirm eligibility
- obtain vital signs
- conduct a physical examination
- conduct a neurological exam
- collect central laboratory samples (hematology and chemistry)
- collect serum pregnancy sample in women of childbearing potential (done at the central laboratory)*
- collect urine for central lab urinalysis
- collect urine for pregnancy test (must be confirmed negative prior to dispensing study drug)*

* If the urine pregnancy test result is negative and the serum pregnancy test result is positive, the patient is to be contacted and the following actions are to take place:

- instruct the patient to discontinue taking study drug
- schedule the patient for an unscheduled visit to collect another serum pregnancy test

The serum pregnancy test result will be used to determine the patient's eligibility to continue receiving study treatment. See section 17.5.2.1 regarding how pregnancies are to be handled in this study.

- obtain blood for PK
- at select sites only, perform skin biopsy (optional). Obtain 3 samples (i.e., H&E, nerve fiber density (histology) and MOR/KOR density (histology, Western Blot)); see the Lab and Study Reference Manuals for details
- perform 12-Lead ECG after at least 5 minutes in a supine position (See the Study Reference Manual for ECG procedures, section 17.4 Electrocardiograms for the handling of Cardiovascular adverse events)
- record AEs
- review of concomitant medications, including over-the-counter medications, nutritional supplements, and vitamins; also collect the TR03 rescue medication log

- retrieve any remaining study drug from the parent study TR03
- administer the Worst itch NRS and **review score for eligibility to either enter the Treatment Period or to continue in screening under the Observation Period**
 - a) If the Worst Itch NRS score is < 5 , start the Observation Period. Do NOT initiate study drug treatment at this visit
 - b) If Worst Itch NRS score is ≥ 5 , confirm eligibility and start the Treatment Period (see below, 'For patients qualifying for drug Treatment Period only').

The Worst Itch NRS must be administered at the study site under the supervision of and by trained study staff, strictly adhering to PRO Administration Instructions (see Study Reference Manual)

For patients qualifying for the drug Treatment Period only (Visit 1a is also study visit TV1):

- complete PAS
- administer PRO measurements:
 - Average itch intensity NRS
 - VRS
 - ItchyQoL
 - MOS Sleep-R
 - HADS
 - PBI-P

The PRO questionnaires must be administered at the study site under the supervision of and by trained study staff, strictly adhering to PRO Administration Instructions (see Study Reference Manual)

- At selected sites only, perform skin biopsy (optional). Obtain 3 samples (i.e., H&E, nerve fiber density (histology) and MOR/KOR density (histology, Western Blot)); see the Lab and Study Reference Manuals for details
- dispense Study Drug to the patient required until return at Treatment Visit 2, TV2
- dispense the Dosing Diary and instruct the patient on how to complete it
- dispense the Rescue Medication Log and instruct the patient on how to complete it
- instruct patients to self-administer the first dose on the evening of Visit 1a at home
- instruct patients to notify the Investigator if any significant CNS AEs occur, and not to drive or operate dangerous machinery until the effect of the Study Drug can be assessed by the Investigator, see [Section 9.3](#)
- instruct the patient to take the Study Drug twice daily at approximately the same times of day. All patients should be instructed to titrate to their most tolerated dose. See [Table 3](#) Drug Dosing Schedule for more information. Here is the recommended Week 1 titration schedule for patients who tolerate study drug:

Day 1 (the first day that study drug the patient receives a study drug dose): No dose in the AM and 30 mg in the PM

Day 2: No dose in the AM and 30 mg in the PM

Day 3: 30 mg in the AM and 30 mg in the PM

Day 4: 30 mg in the AM and 30 mg in the PM

Day 5: 30 mg in the AM and 60 mg in the PM

Day 6: 60 mg in the AM and 60 mg in the PM

Day 7: 60 mg in the AM and 60 mg in the PM

- instruct patients to bring all remaining Study Drug to the Investigator site for each study visit
- If a patient misses 3 or more consecutive doses, contact the Medical Monitor.

For patients starting the Treatment Period, the next visit will be TV2, Treatment Week 3.

For patients not qualifying for the drug Treatment Period only (Visit 1a is also study visit OV1), the patient will enter the Observation Period and the next visit will be OV2, Extending Screening Week 4 (see [section 9.6.3](#) Observation Period (Extended Screening Weeks 1-12))

9.6.2 Treatment Period (Treatment Weeks 1-50)

Patients who enter the Treatment Period on Visit 1a will be in the Treatment Period for up to 50 weeks and thus are eligible to receive study drug for up to 50 weeks.

Patients who enter the Treatment Period from the Observation Period will be in the Treatment Period for up to 46 Treatment Weeks. Patients enter the Treatment Period from an Observation Visit (OV) when their Worst itch NRS is greater than or equal to 5 (≥ 5).

Regardless of how many treatment weeks the patient was on study drug, all patients who enter the Treatment Period will complete End of Treatment Visit TV14. Since all patients must titrate to their maintenance dose over the first four weeks of the Treatment Period, Visits 1a/Visits 1b (TV 1) and TV 2 over the first four weeks of the Treatment Period will be common to all subjects in TR03ext regardless of when they enter into the Treatment Period. Patients who transition from the Observation Period to the Treatment Period at a respective Observation Visit will follow the Treatment Visit schedule outlined in [Table 8](#).

9.6.2.1 Treatment Period Weeks 2-4 (Titration Phase of Study Drug)

The first week in the Titration phase is initiated as part of Visit 1a/1b (Day 1 Treatment Week 1, see [Section 9.6.1](#) and [Section 9.6.4](#)). Subsequently, the following events TC1, TV2 and TC2 will be conducted during the remainder of the titration phase. See [Table 5](#) for the Schedule of Events during the titration phase.

9.6.2.1.1 Telephone Contact Number 1 (TC1, Treatment Week 2)

The patient is to be contacted by phone and the following are to take place:

- Record AEs
- Reinforce compliance
- Confirm that patient has titrated drug in accordance with the dosing schedule on [Table 3](#)

- Document tolerability/intolerability to study drug and decision to continue dose titration/maintenance following the dosing schedule of [Table 3](#)
- Discontinue study medication in patients who could not tolerate 30 mg BID dose and complete the End of Treatment Visit, TV14 (See [Section 9.6.2.2.12](#) and [Section 11](#))

9.6.2.1.2 TV 2 (Treatment Week 3)

The following procedures are to take place at this visit:

- obtain vital signs
- collect urine for pregnancy (must be confirmed negative prior to dispensing study drug)
- collect blood for PK
- perform 12-Lead ECG after at least 5 minutes in a supine position (See the Study Reference Manual for ECG procedures, [section 17.4](#) Electrocardiograms for the handling of Cardiovascular adverse events)
- perform brief neurological assessment
- administer PRO measurements:
 - Worst itch NRS
 - Average itch intensity NRS
 - VRS
 - ItchyQoL
 - MOS Sleep-R
 - HADS.

The PRO questionnaires must be administered at the study site under the supervision of and by trained study staff, strictly adhering to PRO Administration Instructions (see Study Reference Manual).

- record AEs (including tolerability to study drug)
- review concomitant medications, including over-the-counter medications, nutritional supplements, and vitamins
- reinforce compliance
- perform Study Drug accountability, retrieve previously dispensed Study Drug
- dispense the Study Drug to the patient required until return at TV3 (Treatment Week 5)
- Document tolerability/intolerability to study drug and titration decision based on [Table 3](#)
- Discontinue study medication in patients who could not tolerate 30 mg BID dose and complete the End of Treatment Visit, TV14 (See [Section 9.6.2.2.12](#) and [Section 11](#))

9.6.2.1.3 Telephone Contact Number 2 (TC2, Treatment Week 4)

The patient is to be contacted by phone and the following are to take place:

- record AEs

- reinforce compliance
- instruct the patient on dose titration/maintenance based on [Table 3](#)
- patients reporting intolerable side effects at their current dose should titrate down to a tolerable preceding dose and this should be record as the patient's maintenance dose
- patients at any dose who reported intolerable AEs for the previous week (Week 3 on drug) and continue to report intolerable AEs on this visit, should be discontinued from study drug and scheduled for the End of Treatment Visit, TV14 (See [Section 9.6.2.2.12](#) and [Section 11](#))

9.6.2.2 Treatment Period Weeks 5-50

During this period of the study, the patient continues on the maintenance dose established by the end of Treatment Week 4 for the remainder of the study with the exception of two allowable dose reductions permitted during Treatment Weeks 5 – 50 (e.g., a patient at 90 mg BID can be reduced to 60 mg BID and then subsequently to 30 mg BID). If a third dose reduction is needed, the patient should be discontinued from the study (See [Table 3](#), [Section 9.6.2.2.12](#) and [Section 11](#)). Patients who are on the 30 mg BID dose will be discontinued if a dose reduction is required.

See [Table 6](#) for the Schedule of Events for Treatment Weeks 5-50.

9.6.2.2.1 TV 3 (Treatment Week 5)

The following procedures are to take place at this visit:

- Administer the Worst Itch NRS and evaluate against the Failure-to-Improve criteria (see [Section 11.1](#))
- For patients who MEET the Failure-to Improve criteria
 - Stop study medication
 - Perform End of Treatment Visit (TV14) procedures
- For patients who DO NOT meet Failure-to-Improve criteria, perform the following procedures
 - obtain vital signs
 - collect urine for pregnancy test (must be confirmed negative prior to dispensing study drug)
 - collect blood for PK
 - perform 12-Lead ECG after at least 5 minutes in a supine position (See the Study Reference Manual for ECG procedures, [section 17.4](#) Electrocardiograms for the handling of Cardiovascular adverse events)
 - perform brief neurological assessment
 - administer PRO measurements:
 - Average itch intensity NRS

- VRS
- ItchyQoL
- MOS Sleep-R
- HADS

The PRO questionnaires must be administered at the study site under the supervision of and by trained study staff, strictly adhering to PRO Administration Instructions (see Study Reference Manual).

- record AEs
- review of concomitant medications, including over-the-counter medications, nutritional supplements, and vitamins
- reinforce compliance
- perform study drug accountability, retrieve previously dispensed study drug
- dispense the study drug to the patient required until the next Treatment Visit

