All patients on drug treatment will enter a 2-week wash-out and safety follow up period following end of the Treatment Period with procedures conducted according to the Schedule of Events (See [Appendix 1](#)).

Patients with a Worst Itch NRS score less than 5 (< 5) enter the Observation Period:

Patients with a Worst Itch NRS score < 5 at Visit 1a will enter into an extended screening period, Observation Period (no drug treatment), of the study and will be followed for up to 12 weeks (extended screening weeks). Visit 1a for these patients is also Observational Visit 1 (OV1). Subsequent visits will be defined as OV2, OV3 and OV4 and will occur at approximately monthly intervals for the next 3 months.

During this Observation period, patients who report an increase in their Worst Itch NRS with a score of ≥ 5 at any one of their Observation Visits and meet all other eligibility criteria will be able to enroll immediately into the Treatment Period of the study and Visit 1b procedures are to be performed. Patients will receive open-label Study Drug starting with an evening 30 mg dose (to be taken at home), after the Visit 1b procedures have been completed. Receipt of the first drug will indicate the start of their Treatment Period and enrollment into the study. The duration of the Treatment Period for such a patient will vary depending upon the visit at which they transition from the Observation Period to the Treatment Period.

Patients in the Observation Period whose Worst Itch NRS score remains <5 over the 12 extended screening weeks will be screen failed from the study at the end of that time period.

Failure to Improve Criteria:

Beginning on TV 3 and at every subsequent Treatment Visit, patients with a Worst itch NRS equal to or greater than (\geq) the Worst Itch NRS at Visit 1a (or at Visit 1b in the case of patient who require the Observation Visit period) will be discontinued from taking study drug. Subjects discontinued from taking study drug are to undergo the End of Treatment Visit (TV14), the Washout/Safety Follow-up Period assessment in two weeks and receive a follow-up Telephone Contact 30 days following end of study drug for final safety

	assessment.

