9.6.2.2.12 TV 14 (End of Treatment Visit)

This visit applies to all patients who completed TV13; including patients who met Failure-to-Improve criteria at any Treatment Visit during the study.

For patients who DID NOT meet Failure-to-Improve criteria during the conduct of the study, this visit (TV14) takes place after the patient has completed study medication.

- For patients who entered the Treatment Period at Visit 1a, TV14 would take place during week 51; four (4) weeks after TV13, as these patients should complete 50 weeks of treatment prior to TV14
- For patients who entered the Treatment Period at Visit 1b see [Table 8](#) for information on when TV14 is to take place

The following procedures are to take place at this visit:

- obtain vital signs
- perform physical examination
- perform brief neurological assessment
- complete the PAS
- perform 12-lead ECG after at least 5 minutes in a supine position (See the Study Reference Manual for ECG procedures, [section 17.4](#) Electrocardiograms for the handling of Cardiovascular adverse events)
- collect blood for central laboratory (hematology and chemistry) and serum pregnancy test for central laboratory
- collect urine for urinalysis at the central laboratory
- collect blood for PK
- at select sites only, perform skin biopsy (optional). Obtain 3 samples (i.e., H&E, nerve fiber density (histology) and MOR/KOR density (histology, Western Blot)); see the Lab and Study Reference Manuals for details
- administer PRO measurements:
 - Worst itch NRS
 - Average itch intensity NRS
 - VRS
 - ItchyQoL
 - MOS Sleep-R
 - HADS
 - SOWS

The PRO questionnaires must be administered at the study site under the supervision of and by trained study staff, strictly adhering to PRO Administration Instructions (see Study Reference Manual).

- record AEs

- review of concomitant medications, including over-the-counter medications, nutritional supplements, and vitamins
- perform study drug accountability, final retrieval of any dispensed study drug
- retrieve the Dosing Diary
- Dispense the 14 Day SOWS packet, instruct the patient on how to complete the scales and to complete the scales daily for 14 days
- Schedule the patient for the Washout and Safety Follow-up Period Visit

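### At TV3–TV13 the Worst Itch score is judged before the other questionnaires are given, and patients who fail then rate Worst Itch a second time the same day under TV14, after the stop decision.

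*Protocol*

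**What the plan says.** All references are to protocol Version 2.0 unless stated.

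- **TV3 to TV13 (Sections 9.6.2.2.1 to 9.6.2.2.11).** Under the line "The following procedures are to take place at this visit", the first item is "Administer the Worst Itch NRS and evaluate against the Failure-to-Improve criteria". Two branches follow. For a patient who meets the criterion the items are "Stop study medication" and then "Perform End of Treatment Visit (TV14) procedures". For a patient who does not, the list continues with the ordinary visit procedures, including Average itch NRS, VRS, ItchyQoL, MOS Sleep-R and HADS, with no second Worst Itch.
- **The criterion (Synopsis; Table 3, footnote 6).** From TV3 on, "patients with a Worst itch NRS equal to or greater than" the Visit 1a or 1b score are taken off study drug. A tie with baseline is therefore a failure, and one assessment decides.
- **TV14 (Section 9.6.2.2.12).** The visit applies to patients who met the criterion at any Treatment Visit. Its PRO list starts with "Worst itch NRS" and goes on to Average itch, VRS, ItchyQoL, MOS Sleep-R, HADS and SOWS.
- **Visit 1b (Section 9.6).** In the comparable situation, where a Worst Itch score has just been used as a gate, the text says "Do not repeat the Worst Itch NRS during Visit 1b".
- **Use of the data.** Section 4.2 lists change from baseline in these PROs by the final Treatment Period Visit as a secondary objective. Section 5.2 lists change by Treatment Period visit, and the frequency of failure-to-improve, as secondary endpoints. Section 9.6.3 calls TV14 the final Treatment Period visit.

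**The concern.** These are subjective scales in an open-label study. A patient who has just been taken off drug for not improving is then asked how bad the itch is, how it affects quality of life, sleep and mood, and once more how bad the worst itch was. The answers may reflect the decision as well as the disease.

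The second rating also creates a data problem. One secondary endpoint, failure-to-improve status, rests on the first Worst Itch score of the day. Another, the change in Worst Itch at the final visit, would naturally rest on the second. The two can disagree in the same patient on the same day, and the text available here does not say which score is the final-visit value.

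**Working it through.** No arithmetic applies: the protocol plans no formal testing and has no sample-size calculation. The check is a comparison of sections.

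1. **Is the order imposed, or only a matter of bullets?** Which branch applies at TV3–TV13 depends on the result of the comparison with baseline. The other PROs sit inside the branches. Judging Worst Itch before the other PROs therefore follows from the structure, at all 11 visits. That the drug is stopped before the PROs are completed rests only on list order.

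2. **Is it the same day?** Both items of the failing branch fall under procedures for that visit. Section 9.6.6 is consistent with this: it counts the follow-up call from the visit at which the patient met the criterion and stopped medication.

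3. **Is Worst Itch asked twice?** It is asked once as the gate and once in the TV14 list. Section 9.7.7.1 gives a recall period of the past 24 hours, so both ratings cover essentially the same period. The no-repeat instruction in Section 9.6 covers Visit 1b only.

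4. **Can the two scores conflict?** Let B be the baseline score, W1 the gate score and W2 the TV14 score. The patient fails if W1 ≥ B. Take a tie, W1 = B, and a repeat one point lower, W2 = B − 1. Failure status is then yes, while the TV14 change is W2 − B = −1, an improvement. One point is the smallest step on the 0–10 scale.

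5. **Who is affected?** Only patients stopped by this rule. Patients who never meet it reach TV14 as a scheduled visit after completing drug, and no failure check is listed there.

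6. **Did the order exist before the amendment?** In Version 1.0 (Section 9.6.2.2.1) Worst Itch was given with the other PROs in one block. The split came with its use as a gate in Version 2.0.

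**The case against.** The strongest objection is that the governing text may lie elsewhere. Section 9.6.2.2.1 refers to Section 11.1 for the criterion and to the Study Reference Manual for PRO administration. Neither is in the text available here, nor is Table 6 of Version 2.0. The protocol does place skip rules outside the visit lists, as with Visit 1b. This stands as a caveat: if one of those sources already sets the order or forbids the repeat, the remaining task is to make the visit sections agree with it.

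Next, nothing says the patient is told the result, or is shown the baseline score, before completing the forms. That also stands. Knowledge of the decision is an inference, though a fair one, because the rule compares two of the patient's own ratings and being taken off drug reveals the outcome.

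Third, an analysis rule could choose between the two Worst Itch scores, and the gate score is always taken before the decision. This is true for Worst Itch. It does not help Average itch, VRS, ItchyQoL, MOS Sleep-R or HADS, which have no pre-decision value at that visit. The longer recall periods of ItchyQoL and HADS (past week) and MOS Sleep-R (past 4 weeks) may dampen the effect but do not remove it.

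Three stronger readings are tempting but unsupported.

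- **All final-visit PRO results are compromised.** Only patients stopped by this rule are affected. PBI-P is not in the TV14 list of Section 9.6.2.2.12, the primary endpoint is treatment-emergent adverse events, and no comparison of failing with continuing patients is planned.
- **The bias can be given a size.** The documents give no failure rate, no repeat-rating variability and no shift from knowing the verdict. Any figure would rest wholly on assumptions.
- **Visit 1a has the same flaw.** There too, staff "review score for eligibility to either enter the Treatment Period or to continue in screening under the Observation Period" before the other PROs. But only patients who qualify for treatment complete those PROs, so all of them answer after the same news. Changing that order would be a preference, not a correction.

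**Conclusion.** The point holds in limited form. On the visit sections as written, patients stopped for failure to improve give their TV14 PRO answers after the judgement that stops them, and give two Worst Itch ratings on one day with no rule against the repeat. Their TV14 values are exposed to open-label reporting bias, and their failure status can contradict their TV14 Worst Itch change.

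The consequence is modest: descriptive secondary PRO summaries, in this subgroup only, by an amount the documents do not allow one to estimate. The conclusion assumes that patients can learn the decision before completing the forms, and that no source outside the available text sets a different order. It still merits a change, because the order of data collection cannot be repaired at analysis for the PROs other than Worst Itch.

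**What to change.** In Sections 9.6.2.2.1 to 9.6.2.2.11:

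- Give the full PRO set (Worst Itch, Average itch, VRS, ItchyQoL, MOS Sleep-R, HADS) before anyone reviews the Worst Itch score, then apply the failure-to-improve criterion.
- For patients who meet it, use that same set as the TV14 values and carry out only the remaining TV14 items, such as SOWS, afterwards.

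In Section 9.6.2.2.12, add that the Worst Itch NRS is not repeated when TV14 falls on the same day as the gate assessment, matching the Visit 1b rule. One Worst Itch score then serves as both gate and final-visit value, so the two cannot conflict. Section 11.1, Table 6 and the Study Reference Manual should be checked for agreement.

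The cost is a reordering of forms and a short instruction to sites. Both branches already complete these PROs, so nothing is added at TV3–TV13, and failing patients complete one form fewer. The stopping rule is unchanged, and Visit 1a needs no change.
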